PART B STUDY DESCRIPTION

TITLE OF PROTOCOL	Uniport and multiport epidural catheters in post-surgical patients		
Principal Investigator	[name]		
Co-Investigators	[name], [name] , NP, [name]		
Mailing Address	Department of Anesthesia, Critical Care and Pain Medicine, Beth Israel Deaconess Medical Center, [name]		
E-Mail Address	[contact]		
P.I.'s Telephone	[name]	P.I.'s Pager [name]	Fax:[name]
Sponsor/Funding Source	Beth Israel Anesthesia Foundation		

B1. PURPOSE OF PROTOCOL

Hypothesis:

We hypothesize that multi-port thoracic epidural catheters will provide superior pain relief when compared to uniport catheters for post-surgical patients.

B2. SIGNIFICANCE AND BACKGROUND FOR THE STUDY

Epidural analgesia (pain relief) is an effective treatment for post-surgical acute pain. The factors that determine the effectiveness of pain relief with epidural analgesia have been studied almost exclusively in the lumbar (low back) spaces for obstetrics (childbirth)^{1,2,3,4}. These factors include the design of the epidural catheter, the type and dose of medications, and the volume of solution used. One of the important issues specific to the catheter design is whether the tip has a one end-hole, or multiple side holes. The number of holes has been suggested to affect the spread of epidural anesthetic over time, especially with low volume solutions. This has been demonstrated in older, stiffer epidural catheter designs, but has not been shown to be true with the newer, flexible epidural catheters.

The thoracic (upper back) epidural analgesia is widely employed for a many types of surgical pain. While the mechanism of pain relief is similar to that in the lumbar space, there may be differences between the two sites. Firstly, thoracic catheters tend to use low volume, high concentration medication solutions, which likely do not spread as effectively. Secondly, the thoracic catheters often need to be used for prolonged periods of time. Whereas the typical obstetric epidural is used for less than 12 hours, the post-surgical catheter is typically required for one to three days (or more). Finally, the thoracic space is narrow, with a thinner thecal sac, which might promote a difference in the spread of epidural solution.

Thoracic epidural analgesia is routinely used to control post-operative pain for a wide variety of surgical procedures. Based on the improved effectiveness of the one end-hole flexible epidural catheter in obstetrics, this design is commonly used in thoracic epidural analgesia. It has been observed that thoracic epidurals are somewhat less effective after a period of time when compared to the effectiveness of labor epidurals. This may be in part due to the inappropriate assumption that the

thoracic epidural space of a post-surgical patient is the same as the lumbar space of a parturient.

We seek to determine whether there is a difference in the analgesia provided by an FDA approved thoracic multi-port epidural catheter when compared to an FDA approved thoracic uniport epidural catheter as measured by pain scores, medication given for breakthrough pain, and need to add intravenous opioids. As mentioned previously, these catheters have been studied extensively in laboring patients but there is a striking paucity of literature regarding how anesthetic solutions spread in the thoracic epidural spaces of non-pregnant post-surgical patients and how this may be affected by catheter type. If the hypothesis is supported by results, it may change the practice within the study institution, and possibly, on a much larger scale. This study may also provide a foundation for further research into the physiology of the thoracic epidural space, how it differs from the lumbar epidural space, and how a medication solution spreads within this unique space.

References:

3. Jaime, F, Mandell, GL, Vallejo, MC, Ramanathan, S. "Uniport Soft-tip, Open ended Catheters Versus Multiport Firm-tipped Close-ended Catheters for Epidural Labor Analgesia: A Quality Assurance Study. *Journal of Clinical Anesthesia*. 12:89-93. 2 200.

B3. DESCRIPTION OF RESEARCH PROTOCOL**A. Study Design – Overview, Methods, Procedures**

This will be a double blind, prospective randomized trial to compare the effectiveness of uniport vs multiport thoracic epidural catheters. An investigator will approach patients who are to undergo a surgical procedure with a request for thoracic epidural analgesia. Inclusion criteria will include English speaking, surgery in the thorax or upper abdomen, age between 18 and 75, and expected use of epidural analgesia for >24 hours. Exclusion criteria will include contraindication to epidural catheterization, chronic use of opioids, chronic pain, allergy to the standard medications used for epidural pain relief, incarceration, Body Mass Index >40, delirium, dementia, or other mental status which would make follow-up impossible. All patients will receive informed written consent by an investigator.

After informed written consent is obtained, the patients will be randomized to receive either a flexible multiport catheter or a flexible uniport catheter in the thoracic space. The anesthesia team providing care to the subject will then place the epidural. The APS NP that will follow the subject post operatively will be blinded to the catheter type (these catheters look the same when in place). An appropriate epidural test dose will be used to confirm non-intravenous or intravascular placement. The patient will be assessed for a change in sensory level approximately 10 minutes after administration of test dose to ensure that the epidural catheter is in the epidural space. The epidural will then be taped in place per normal protocol such that the different epidural catheter types will not be identifiable (except for when the epidural is finally removed).

Intraoperative Management:

All epidural infusions will be started intraoperatively at a rate of 6 mL/hr of standard APS 10 epidural solution. The rate of the epidural intraoperatively will then be titrated from 6-12mL/hr at the discretion of the anesthesiologist performing the case. The epidural will not be shut off for hypotension unless the patient is persistently hypotensive despite adequate fluid resuscitation and vasopressor treatment.

Postoperative management:

All patients will receive a continuous infusion of APS 10 solution (includes bupivacaine and hydromorphone) at a rate between 6 and 12 ml per hour in the PACU. The postoperative nurse using current practice guidelines for all patients will adjust the postoperative infusion rate appropriately. Once the patient is comfortable with an appropriate epidural infusion, they will be transferred to the post-surgical floor.

In the event of uncontrolled pain the following protocol will be employed:

1. A sensory coverage level should be checked using ice. The epidural position and connections should also be verified.
2. If the provider believes the epidural is still appropriately placed the epidural should be bolused with 5 mL APS 10 assuming hemodynamic stability. If the patient is on the floor the epidural infusion rate can be increased by 5 -10 mL/hr for 1 hr then returned to the typical range. This may be repeated to give a second bolus.
3. If the practitioner believes that the catheter was placed too deep in the epidural space the catheter may be pulled back but should not be pulled back more than 2 cm from the

original position.

4. If the patient has a sensory level that isn't completely covering the area of pain consider increasing the rate of the infusion.
5. If the patient continues to have pain the patient may be started on IV/PO Acetaminophen if the patient has no contraindications to this drug.
6. Consider addition of NSAIDs and/or gabapentin.
7. If the patient continues to have inadequate pain control refractory to the above then one can consider splitting the epidural (adding an enteral or IV Opioid).

Assessments:

The primary outcome of the study will be the incidence of failed epidural analgesia, defined as the need to add intravenous opioids or halting or replacing the epidural catheter because of lack of pain control. Other outcomes that will be measured include the incidence of supplemental treatments, the required dose of medication (hourly average), need for treatment of side effects, and complications.

All patients will be assessed for pain using an 11-point visual analogue scale. Sensory level will be recorded daily as will any episodes of breakthrough pain. Sensory level will be assessed with a change in perception to ice. All assessments will be performed preoperatively, in the PACU (when the patient is deemed to be awake, alert and responding appropriately), and on each subsequent postoperative day until the catheter is removed per the standard nursing epidural policy.

B. Statistical Considerations

Sample Size Justification: Based on the expected differences in efficacy, power analysis was performed (PS software, Vanderbilt University) using $\alpha=0.05$, $\beta=0.80$ and incidence of epidural failure (primary endpoint) difference of 20% (no current studies, estimated from previous experience), we estimate that 91 patients would be needed per group. We would plan to enroll 120 patients per group (240 patients total) to account for drop out due to epidural catheter misplacement, accidental dislodging, or halting of the epidural due to side effects, such as low blood pressure. Drop out rate should be minimal given that all of these patients will be inpatients on surgical wards that will not require post-discharge follow up.

Data Analysis: All continuous data (e.g. secondary endpoints of pain scores) will be assessed for normality using the Shapiro-Wilke test. Comparisons between the primary outcome (epidural failure) will be performed using Fisher's exact test (or chi square depending on effect size). Time to epidural failure for each catheter will be plotted on a failure vs time curve (like a survival curve). Comparison of other outcomes will be performed using the t-test, Mann-Whitney test, Fisher's exact, as appropriate. Duration of epidural analgesia (time to halting) will be analyzed using log-rank analysis. Finally, we will perform a logistic regression to attempt to determine factors that may be associated with epidural analgesia failure. The data will be stored electronically on secure BIDMC servers behind the firewall. The computations will be done using STATA and/or SPSS. The above plan was made in conjunction with biostatistician [name], SCD.

C. Subject Selection

Selection: Patients who are to undergo a surgical procedure with a request for thoracic epidural analgesia will be approached by an investigator. Additionally, the acute pain resident and/or nurse practitioner will look through the daily OR schedule to identify patients that may benefit from thoracic epidurals and discuss with the primary anesthesia team whether this is included in their anesthetic plan. Inclusion criteria will include English speaking, surgery in the thorax or upper abdomen, age between 18 and 75, and expected use of epidural analgesia for >24 hours. We are expecting the racial, ethnic and gender composition of our sample to be representative of the typical BIDMC Boston campus aggregate patient population. Exclusion criteria will include contraindication to epidural catheterization, chronic use of opioids, chronic pain, allergy to the standard medications used for epidural pain relief, incarceration, Body Mass Index >40, delirium, dementia, or other mental status which would preclude providing own informed consent. Women of childbearing age will not be excluded from this study. All patients would receive informed written consent by an investigator.

B4. POSSIBLE BENEFITS

Benefits: Possible benefits include improved pain control following extensive surgical procedures involving the thorax and/or upper abdomen. Our belief is that the smaller/thinner thoracic epidural space will be disproportionately affected by a slightly misplaced end hole (uniport) epidural catheter and that there is a real possibility that the spread of anesthetic solution from a multiport epidural catheter will be superior. If we demonstrate that multiport catheters are superior in our study group this would very likely change standard of care from uniport catheters to using multiport epidural catheters for thoracic epidural analgesia not only at our institution but hopefully on a much larger scale (nation and world wide). Given the many thousands of thoracic epidurals placed annually in the U.S. a 20% (what we're predicting) improvement in analgesia could provide profoundly better pain relief to future post-surgical patients.

B5. POSSIBLE RISKS AND ANALYSIS OF RISK/BENEFIT RATIO

We believe the primary risks should be identical to the risks for any thoracic epidural. We do not believe that any of our patients will be at any increased risk from receiving a multiport catheter when compared to receiving a uniport catheter (or vice versa). Thus, we believe this to be a minimal risk intervention. We do not anticipate any risks above what patients already have for our current thoracic epidural analgesia procedures. These risks include, but are not limited to, bleeding, infection, post dural puncture headache (when dura accidentally penetrated – happens in about 1% of epidural placements). Risks of any nerve injury or spinal cord injury are extremely rare (probably less than 1:50,000).

Should any of the participants experience any of the above side effects they would be offered, as always, appropriate treatment such as an epidural blood patch for inadvertent dural puncture. Should any participants experience any unexpected psychological effects we would ask our Psychiatric

colleagues to see the patient in addition to providing extensive support and empathy.

Given the possibility of significantly increased pain control in post-surgical patients and the low risk of this intervention we believe that benefit significantly outweighs the risk.

B6. RECRUITMENT AND CONSENT PROCEDURES

Recruitment

Generally, the anesthesia team providing care to the patient (not the acute pain team which will be consulted post-operatively to manage the epidural) will determine whether the patient will benefit from post-operative epidural analgesia. Patients who are to undergo a surgical procedure with a request for thoracic epidural analgesia will be approached by an investigator. Inclusion criteria will include English speaking, surgery in the thorax or upper abdomen, age between 18 and 75, and expected use of epidural analgesia for >24 hours. Exclusion criteria include contraindication to epidural catheterization, chronic use of opioids, chronic pain, allergy to the standard medications used for epidural pain relief, incarceration, Body Mass Index >40, delirium, dementia, or other mental status which would make follow-up impossible. All patients would receive informed written consent by an investigator.

Consent

Both verbal and written consent will be obtained directly from the patient. Consent will be obtained after the patient has been consented by the primary team for general anesthesia and epidural analgesia. The consent for the study will take place in the holding area, in a private setting, prior to administration of any sedatives/anxiolytics. We do not feel that it will be possible to obtain consent/thoroughly discuss the study with prospective patients prior to the day of surgery given the complex nature of the decision by the primary anesthesia team to place a thoracic epidural (many patients who are eligible inevitably don't receive thoracic epidurals for a wide variety of reasons). Risks, benefits, alternatives and lack of penalty for opting out will all be thoroughly discussed. Our written consent form has been drafted and is included in this application.

Subject Protection

No vulnerable subjects have been identified for this study. However, patients undergoing the types of procedures that require post-operative thoracic epidural analgesia tend to be patients with significant disease (i.e. Whipple for pancreatic cancer, thoracotomy for lung cancer). Patients who cannot consent for themselves will be excluded from the study because they may not reliably be able to communicate pain scores and other subjective measures.

B7. STUDY LOCATION

Privacy

Patients will be screened in a private area in the pre-op holding area. Once enrolled the study specifics and consent will be placed in the confidential patient chart. All patient data will be collected and maintained on secure BIDMC servers behind the firewall. No follow up will be necessary following removal of the epidural and discharge from the hospital.

Physical Setting

This study will take place in the pre-op holding area, the post anesthesia care unit and the patient's room. All of these locations have the ability to create a private space to confidentially discuss patient information. No further clinical follow up will be necessary following discharge from the hospital.

B8. DATA SECURITY

All data will be kept electronically on the BIDMC servers behind the firewall. No data will be stored on local hard drives of personal computers, tablets or smart phones. All paper data will be secured in the confidential paper chart or secured in the locked anesthesia office.

B9 Multi-Site Studies

Is the BIDMC the coordinating site or is the BIDMC PI the lead investigator of the multi-site study?
 Yes No

B10 Dissemination of Research Results

All patients will be queried as to whether they would like the final results of the study. Those who indicate they would like results will receive an email when results are available. All patients will receive a written thank you from the investigators following completion of the study.

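### Randomisation comes before the epidural is attempted, with no step concealing catheter type from the placing team until the space is found; opening the allocation then would avoid pre-insertion losses and limit operator influence

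*Combined protocol and SAP*

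**What the plan says.** Section B3.A gives the order of events. First: "After informed written consent is obtained, the patients will be randomized to receive either a flexible multiport catheter or a flexible uniport catheter". Next: "The anesthesia team providing care to the subject will then place the epidural". Position is checked only once the catheter is in: "The patient will be assessed for a change in sensory level approximately 10 minutes after administration of test dose".

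On blinding, the same section opens with "This will be a double blind, prospective randomized trial". The one person it names as blinded is the postoperative nurse practitioner: "The APS NP that will follow the subject post operatively will be blinded to the catheter type". The reason given is that "these catheters look the same when in place", which does not cover the time before insertion. The document describes no method of allocation concealment and does not say when, how or to whom the allocation is disclosed.

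Section B3.B raises 91 patients per group to 120 "to account for drop out due to epidural catheter misplacement", accidental dislodging, or halting for side effects. It defines no analysis population and gives no rule for a randomised patient without a working catheter.

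**The concern.** The arms differ only in the catheter, so failure to reach the epidural space cannot be an effect of catheter type. Under the planned order, a patient in whom that happens has already been randomised. Excluding the patient departs from the comparison as randomised. Keeping the patient adds someone who received neither device and does not fit the primary outcome. That outcome (B3.A, Assessments) is written in terms of adding intravenous opioids to an epidural, or of stopping or replacing one.

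The second issue is influence. If the operator knows the type while choosing the interspace and deciding whether to persist, effort and abandonment could differ by arm. Section B4 records a directional belief: the investigators expect a slightly misplaced single-hole catheter to suffer more in the thoracic space. Care in placement is therefore a step at which expectation could affect the result. If abandonment differed by arm and those patients were then excluded, the remaining groups would no longer be comparable by randomisation.

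**Working it through.** **1. The plan's own figure.** Inputs from B3.B: alpha 0.05 (taken as two-sided), power 0.80 (the text's beta of 0.80 read as power), a 20-point difference (read as absolute), 91 per group needed, 120 enrolled. Arm rates are not given, so they are assumed.
- 40% v 20%, pooled variance: n = [1.960·√(2·0.3·0.7) + 0.842·√(0.24 + 0.16)]² / 0.2² = 81.2. With continuity correction: (81.2/4)·[1 + √(1 + 4/(81.2·0.2))]² = 90.9, so **91**.
- 50% v 30%, unpooled variance: (0.25 + 0.21)·(1.960 + 0.842)² / 0.04 = 90.3, so **91**.

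The figure of 91 is reproduced under either assumption.

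**2. The allowance for loss.** 1 − 91/120 = 24.2%, or 29 per group. The document does not split this by cause. Dislodging and halting for side effects need a catheter in place, and misplacement is checked after the test dose. No pre-insertion share is stated, so the share d must be assumed.

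**3. Power with the same 240 consented patients.** Exact power of the two-sided Fisher test at 0.05, with 40% v 20% failure among patients who receive a catheter and d equal in both arms:
- Planned order, never-placed patients kept as non-failures: 120 per arm, rates 0.40(1 − d) v 0.20(1 − d).
- Later randomisation: 120(1 − d) per arm, rates 0.40 v 0.20.

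| d | Kept as non-failures | Randomised later (n per arm) | Gain, from unrounded values |
|---|---|---|---|
| 0 | 90.8% | 90.8% (120) | 0 |
| 5% | 88.6% | 89.2% (114) | 0.6 points |
| 10% | 86.1% | 87.1% (108) | 1.1 points |
| 15% | 83.1% | 85.4% (102) | 2.3 points |

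**4. How far this depends on the assumptions.**
- If never-placed patients are excluded, the analysed numbers are the same 114, 108 and 102, so there is no power gain. What differs is that the exclusions came after randomisation.
- If they are counted as failures, the rates become 0.40(1 − d) + d v 0.20(1 − d) + d. Power is then 85.3, 79.7 and 73.5%, and the gaps are wider: about 3.9, 7.4 and 11.9 points.
- At 50% v 30% with non-failure counting, power is 83.8, 80.0 and 75.9%. Later randomisation gives 84.5, 82.1 and 80.6%, a gain of about 0.7, 2.1 and 4.7 points.
- Holding power at 90.8% means randomising a full 240, so consenting 240/(1 − d) = 253, 267 or 283 patients.

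**The case against.** Randomising after consent and before the intervention is conventional and valid. The enrolment margin is generous: under 40% v 20% with non-failure counting, power is still 83.1% at 15% never placed, above the 80% target. Postoperative follow-up is by a blinded nurse practitioner. Section B5 regards the two catheters as equal in risk, and nothing in the document shows that hole number changes placement effort. The operator must handle the catheter to thread it, so later opening shortens operator unblinding but does not end it. All of this stands, and it makes the point a modest one.

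A reader might also infer three stronger things that the document does not support.
- That allocation is disclosed at consent, so the operator does know it while finding the space. The text fixes only the order of randomisation and placement. Early disclosure is permitted, not stated.
- That the whole 24.2% allowance could be recovered. The listed causes are, on their natural reading, events after insertion, and later randomisation would not prevent them.
- That the remark in B6, Consent, that "many patients who are eligible inevitably don't receive thoracic epidurals for a wide variety of reasons" shows a large loss after randomisation. It explains why study consent waits until the day of surgery, after the primary team's own consent for the epidural. That timing already keeps much of this attrition out of the trial, so the remainder may be small.

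**Conclusion.** The point holds as an inexpensive improvement, not a flaw that threatens the trial. Two things are established: randomisation precedes the attempt, and no described step conceals catheter type from the placing team until the space is found. It follows that a patient whose space is never reached is already randomised, with no stated rule for analysis.

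The size of the problem cannot be read from the document, because neither the pre-insertion loss rate nor the arm failure rates are given. Under 40% v 20%, equal loss in both arms and non-failure counting, the power at stake is about 0.6 to 2.3 points for 5 to 15% never placed. It is nil if those patients would be excluded and larger if they would be counted as failures. The stronger argument is bias: later opening removes pre-insertion exclusions from the randomised set and removes the chance for known allocation to affect the search for the space. Whether such influence would occur is a possibility, not something the document shows.

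**What to change.** Leave consent as it is. Replace the randomisation sentence in B3.A with one stating that:
- allocations are held in sequentially numbered, sealed opaque envelopes;
- the next envelope is taken and opened only when the team has identified the epidural space, immediately before threading the catheter;
- patients in whom the space is not reached are not randomised.

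Report the number consented but not randomised.

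This leaves losses after insertion untouched. B3.B still needs a stated analysis rule for misplacement found by the test dose, dislodging and halting for side effects, and B3.A should say who is blinded and from when.

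The cost is one protocol sentence, both catheter types at hand for each placement, and a team member already present to open the envelope. If 240 randomised patients are still wanted, somewhat more than 240 must be consented.

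### The drop-out allowance implies, without saying so, that some randomised patients leave the primary comparison; no analysis set is named and the failure definition is given no precedence over drop-out

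*Combined protocol and SAP*

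**What the plan says.** **Order of events.** Section B3.A (Study Design) randomises after consent and only then has the catheter inserted: "The anesthesia team providing care to the subject will then place the epidural". A sensory check about 10 minutes after the test dose is meant "to ensure that the epidural catheter is in the epidural space".

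**Endpoint.** B3.A (Assessments) makes the primary outcome failed epidural analgesia, "defined as the need to add intravenous opioids or halting or replacing the epidural catheter because of lack of pain control". Scheduled assessments take place preoperatively, in the PACU, and "on each subsequent postoperative day until the catheter is removed".

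**Sample size.** B3.B (Sample Size Justification) needs 91 per group and enrols 120, the increase being for "drop out due to epidural catheter misplacement, accidental dislodging, or halting of the epidural due to side effects, such as low blood pressure". It adds: "Drop out rate should be minimal given that all of these patients will be inpatients on surgical wards".

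**Analysis.** B3.B (Data Analysis) gives the test but no population: "Comparisons between the primary outcome (epidural failure) will be performed using" Fisher's exact test or chi-square. Separately, "Duration of epidural analgesia (time to halting) will be analyzed using log-rank analysis".

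**The concern.** Patients who stay in the primary comparison do not need replacing. Enrolling 29 more per group to cover three named events therefore suggests that patients with those events are not counted. Each event arises after allocation, so leaving these patients out gives up the protection of randomisation.

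The same patient can also fit two descriptions. A dislodged catheter followed by intravenous opioids is a failure under the endpoint definition and a drop-out under the sample size paragraph. Two analysts could code that patient differently and both cite the plan. A halt for side effects is not in itself a failure, because the definition ties halting to lack of pain control, but intravenous opioids needed afterwards might be.

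The losses may be related to outcome and to arm. Under B3.A (Postoperative management), the first step for uncontrolled pain is to check the catheter's position and connections, so displacement may be found because analgesia is failing. B4 states the investigators' belief that slight misplacement harms the uniport catheter more. Misplacement is not defined: it could mean only a catheter outside the epidural space, found at the test-dose check, or it could include the slight misplacement of B4. On the second meaning, exclusion would remove part of the effect under study.

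**Working it through.** **Inputs from the documents:** 91 needed and 120 enrolled per group; α = 0.05; a 20% difference in failure, read as 20 percentage points; β printed as 0.80, read here as 80% power.

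**Assumptions (not in the documents):** two-sided testing, the failure rate in each arm, and every event rate below.

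**1. The plan's own figure.** For 40% v 20%, mean 0.30:

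n = [1.960·√(2·0.30·0.70) + 0.842·√(0.40·0.60 + 0.20·0.80)]² / 0.20² = 81.2

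With continuity correction: (81.2/4)·[1 + √(1 + 4/(81.2·0.20))]² = 90.9, that is 91.

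Other pairs also fit (47% v 27% without the correction), so 40% v 20% is one pair consistent with 91 and not the plan's stated rates.

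**2. The allowance.** 120 − 91 = 29, and 29/120 = 24.2%. This is a cushion, not an expected rate.

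**3. What exclusion does.** Let p be the failure rate among all randomised, d the share excluded, and s the share of those excluded who are failures. The retained failure rate is (p − s·d)/(1 − d) in about 120(1 − d) patients. Power and rejection are two-sided exact Fisher probabilities by full binomial enumeration.

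*(a) True difference 40% v 20%, all excluded patients failures (s = 1).* With all 120 per arm, power is 91%.

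| Excluded, uniport/multiport | Retained n | Retained failure | Difference | Power |
|---|---|---|---|---|
| 3%/1% | 116/119 | 38.1% v 19.2% | 19.0 points | 88% |
| 6%/2% | 113/118 | 36.2% v 18.4% | 17.8 points | 86% |
| 12%/4% | 106/115 | 31.8% v 16.7% | 15.2 points | 73% |

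First row: (0.40 − 0.03)/0.97 = 0.381 and (0.20 − 0.01)/0.99 = 0.192.

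*(b) No true difference, 40% in both arms.* With all 120 per arm, rejection is 3.9% at the nominal 5%.

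| Excluded, uniport/multiport | s = 100% | s = 70% | s = 50% |
|---|---|---|---|
| 2%/6% | 6.1% | 4.8% | 4.4% |
| 5%/15% | 19.5% | 7.7% | 4.5% |

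At 5%/15% with s = 100%, retained failure is 0.35/0.95 = 36.8% v 0.25/0.85 = 29.4%. With s = 40%, which means exclusion unrelated to failure, rejection is 4.1%. At 1%/3% with s = 100% it is 4.7%. If d and s are equal in the two arms, the retained rates are equal and no spurious difference arises.

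Case (b) puts more exclusions in the multiport arm, the reverse of (a) and of the belief in B4. The two-sided figure is the same with the arms swapped, but the spurious advantage would then go to uniport.

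**4. What keeping everyone costs.** Suppose 40% v 20% holds only in patients without an event, and a share e has one in each arm. The rates become p(1 − e) if events are scored non-failure, or p(1 − e) + e if scored failure. Power at 120 per arm:

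| e | Scored non-failure | Scored failure |
|---|---|---|
| 5% | 89% | 85% |
| 10% | 86% | 80% |
| 24.2% | 77% | 59% |

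**The case against.** Exclusion is nowhere ordered. The quoted sentence is a sample size cushion, the test sentence removes nobody, and extra patients could equally be enrolled because some will dilute the contrast while still being analysed. That is fair: the defect is silence combined with a suggestive allowance. A reader might infer that the plan mandates a per-protocol analysis; the documents do not say so.

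A reader might also infer that no scoring rule exists. The Assessments section gives one. What is missing is its precedence over drop-out, the analysis set, and how a patient is scored after losing the catheter early, since scheduled assessments end at removal.

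The plan expects few drop-outs, and with few the effect is slight. That arithmetic stands. But the reason offered is inpatient status without post-discharge follow-up, which concerns loss to follow-up and not how often catheters are misplaced, dislodged or stopped. Equally, 24.2% should not be read as the rate the investigators expect.

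The strongest objection concerns size. The 19.5% figure needs a threefold imbalance between arms and every excluded patient a failure, which fits poorly with side-effect halts. At a 70% share it is 7.7%, and at 50% it is 4.5%. A reader might infer that exclusion would manufacture a multiport benefit; the documents give no basis for that direction, and exclusion could as easily shrink a real one.

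Finally, the log-rank analysis of time to halting may use these patients, but it does not settle who enters the primary test.

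**Conclusion.** The concern holds in this form: randomised patients are described as drop-outs for events after allocation, some of which can meet the failure definition, and the plan neither names the analysis set nor says which description prevails. Exclusion is the natural inference, not a stated rule.

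The direction and size of any bias cannot be known from the documents. On the assumed rates, power under a true 40% v 20% difference moves from 91% to between 88% and 73%. A materially raised false-positive rate appears only when exclusions are frequent, unequal between arms and mostly failures. This should be fixed before the data are seen. It is not a fatal flaw.

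**What to change.** - Make the primary Fisher or chi-square comparison all randomised patients in their allocated catheter group.
- Apply the existing failure definition to every patient and state that it takes precedence over drop-out. A patient who meets it is a failure, including through intravenous opioids needed for pain after misplacement, dislodgement or an unplanned side-effect halt. Every other patient is a non-failure.
- Stop counting at planned catheter removal. For patients who lose the catheter early, use inpatient chart records up to a cut-off fixed in advance, preferably abstracted by someone not told the catheter type.
- Define misplacement and report the three events by arm.
- Keep two sensitivity analyses: the events excluded, and all of them counted as failures.
- Reword the 91-to-120 sentence so that all 120 per group are analysed.

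A simpler rule, scoring any intravenous opioid in a fixed window such as 72 hours, should be avoided. B2 expects catheters to be needed for one to three days, so planned removals would fall inside the window, and opioids given after them are not clearly failed epidural analgesia. If an assumed 10%, 20% or 30% of non-failures received such opioids, the rates would become 0.40 + 0.60·share v 0.20 + 0.80·share, and power would fall from 91% to 80%, 66% or 52%.

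The cost is analysis-plan wording, chart abstraction for patients who lose the catheter early, and the dilution shown above: power of 80% to 89% with 5% to 10% events. On that route, extra patients could be needed only if events came near the full 24.2% allowance.
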